## List of figures

Figures 1	Study protocol (PASAT: Paced auditory serial addition task, SDMT: single digit modalities test, FACS: Flow assisted cell sorting, flow cytometry).....	14
-----------	--	----

List of abbreviations

AE	adverse event
ALT	alanine aminotransferase
AST	aspartate aminotransferase
b.i.d.	twice a day
CRF	Case Report/Record Form (paper or electronic)
CPO	Country Pharma Organization
CRO	Contract Research Organization
DS&E	Drug Safety & Epidemiology
ECG	Electrocardiogram
EDC	Electronic Data Capture
ICH	International Conference on Harmonization of Technical Requirements for Registration of Pharmaceuticals for Human Use
IEC	Independent Ethics Committee
i.v.	intravenous
IRB	Institutional Review Board
o.d.	once a day
p.o.	oral
SAE	serious adverse event

## Glossary of terms

Assessment	A procedure used to generate data required by the study
Control drug	Drugs(s) used as a comparator to reduce assessment bias, preserve blinding of investigational drug, assess internal study validity, and/or evaluate comparative effects of the investigational drug
Enrollment	Point/time of patient entry into the study; the point at which informed consent must be obtained (i.e. prior to starting any of the procedures described in the protocol)
Epoch	The planned stage of the subjects' participation in the study. Each epoch serves a purpose in the study as a whole. Typical epochs are: determination of subject eligibility, wash-out of previous treatments, exposure of subject to treatment or to follow-up on subjects after treatment has ended.
Investigational drug	The drug whose properties are being tested in the study; this definition is consistent with US CFR 21 Section 312.3 and is synonymous with "investigational new drug" or "investigational medicinal product."
Investigational treatment	All investigational drug(s) whose properties are being tested in the study as well as their associated treatment controls. This includes any placebos, any active controls, as well as approved drugs used outside of their indication/approved dosage or tested in a fixed combination. Investigational treatment generally does not include other treatments administered as concomitant background therapy required or allowed by the protocol when used within approved indication/dosage
Medication number	A unique identifier on the label of each investigational/study drug package in studies that dispense medication using an IRT system
Subject Number	A number assigned to each patient who enrolls into the study
Part	A subdivision of a single protocol into major design components. These parts often are independent of each other and have different populations or objectives. For example, a single dose design, a multiple dose design that are combined into one protocol, or the same design with different patient populations in each part.
Period	A subdivision of a cross-over study
Premature patient withdrawal	Point/time when the patient exits from the study prior to the planned completion of all investigational/study treatment administration and all assessments (including follow-up)
Randomization number	A unique identifier assigned to each randomized patient, corresponding to a specific treatment arm assignment
Stop study participation	Point/time at which the patient came in for a final evaluation visit or when study/investigational treatment was discontinued whichever is later
Study drug/ treatment	Any single drug or combination of drugs administered to the patient as part of the required study procedures; includes investigational drug (s), active drug run-ins or background therapy
Study/investigational treatment discontinuation	Point/time when patient permanently stops taking study/investigational treatment for any reason; may or may not also be the point/time of premature patient withdrawal
Variable	Information used in the data analysis; derived directly or indirectly from data collected using specified assessments at specified time points

## Protocol synopsis

Protocol number	CFTY720DTR04
Title	Effects of Fingolimod (Gilenya®) on Cytokine and Chemokine Levels in Relapsing Remitting Multiple Sclerosis Patients
Brief title	Effects of Fingolimod (Gilenya®) on Cytokine and Chemokine Levels in Relapsing Remitting Multiple Sclerosis Patients
Sponsor and Clinical Phase	Novartis Phase IV
Investigation type	Drug
Study type	Interventional
Purpose and rationale	
The main purpose of this study is to measure the serum levels of major Th1, Th2, Th17 and Treg cytokines as well as cytokines and chemokines that are known to be upregulated during multiple sclerosis relapses. Measurements will be performed at 3 time points; i.e. before treatment, 12±1 weeks and 24±2 weeks after fingolimod treatment. By this way, we will be able to test whether fingolimod treatment shifts the cytokine balance from Th1/Th17 to Th2/Treg and reduces the levels of inflammation related cytokines and chemokines. The basal levels of the cytokines will be compared with the cytokine levels of healthy controls.
 
The second purpose of the study is to test the predictive value of cytokine/chemokine changes measured in the 3rd and 6th months on the EDSS, PASAT, SDMT, 9-hole peg test, timed 25-foot walk test and relapse rate observed after 6 months of treatment.
 
This study design is not randomized or double blind, but it has no bias since the patients themselves will be their own controls if they fulfill the enrollment criteria.
 
This study was designed since there is accumulating evidence that Th1 and Th17-type immunities play major roles in multiple sclerosis pathogenesis in the last decade. By contrast, Th2 and Treg cytokines appear to counterbalance the production of Th1 and Th17 cytokines and thus play an ameliorating role in the natural course of multiple sclerosis. Not surprisingly, many multiple sclerosis medications exert their beneficial effects through modulation of these cytokines. The effects of fingolimod on cytokine production are largely unknown. So this study was designed to see to evaluate the effects of fingolimod on cytokine production.

Primary Objective(s) and Key Secondary Objective	Primary objective of this study is: -To evaluate the differences between serum cytokine and chemokine levels of healthy controls and multiple sclerosis patients.

Secondary Objectives	
Secondary objective of this study is:
 
-To test the predictive value of cytokine/chemokine changes measured in the 3rd and 6th months on the PASAT, SDMT, 9-Hole peg test, timed 25-foot walk, EDSS and relapse rate observed after 6 months of treatment.

Study design	This study is a multi-center, open label study.
Population	80 relapsing remitting MS (RRMS) patients will be recruited according to the McDonald's criteria and 60 healthy controls will be recruited as the control group. All subjects will sign an informed consent that will be approved by the local Ethics Committee and the applicable health authorities prior to venipuncture. Basal EDSS, relapses during the last 2 years, paced auditory serial addition task (PASAT), 9-Hole peg test, timed 25-foot walk and single digit modalities test (SDMT) scores will be recorded before study entry. Serum and blood samples will be collected from each participant after evaluation for inclusion and exclusion criteria. Additional serum and blood samples at 2 different time points will be collected from MS patients at months 3 ( $\pm 1$ week) and 6 ( $\pm 2$ weeks) after starting fingolimod 0.5 mg/day po. treatment.
Inclusion criteria	

1. Written informed consent must be obtained before any assessment is performed.

2. RRMS patients aged between 18-65 years that fulfill following criteria:

a) In non-treated/newly-diagnosed patients with two or more serious attacks within one year or three or more serious attacks within two years and one or multiple gadolinium-enhancing lesions in cranial MRI or with significantly increased T2 lesions compared to the previous MRI.

b) In non-responders despite treatment with a beta-interferon or glatiramer acetate with adequate duration and dose, where:

a. adequate treatment duration is at least 1 year and,

b. non-responders are patients with no changes in attacks or increased number of attacks after one year of treatment, or with more severe attacks, or those with one or multiple contrast enhancing lesions in cranial MRI or where there is an increase in T2 lesions identified with successive MRI's.

c) In RRMS patients who are unable to tolerate first-line treatments due to adverse effects associated with parenteral administration.

3. Last relapse of the patient should be at least 2 months before study entry.

4. Last steroid dose of the patient should be at least 1 month before study entry.

5. Last interferon or glatiramer acetate dose of the patient should be at least 1 month before study entry.

	
6. Last cyclophosphamide, mitoxantrone, teriflunamide, natalizumab and azathioprine dose of the patient should be at least 3 months before study entry.
 
Inclusion Criteria for Healthy Control Group
 

1. Healthy subjects who don't have any autoimmune disease and aged >18.

2. Written informed consent must be obtained before any assessment is performed.

Exclusion criteria	
Patients fulfilling any of the following criteria are not eligible for inclusion in this study. No additional exclusions may be applied by the investigator, in order to ensure that the study population will be representative of all eligible patients.
 

1. Patients with secondary progressive MS.

2. Patients with known contraindications for fingolimod treatment.

3. Other coexistent autoimmune diseases including Hashimoto thyroiditis, systemic lupus erythematosus, rheumatoid arthritis, psoriasis etc.

4. Patients with any of the following cardiovascular conditions:

• Resting heart rate < 45 bpm/min

• Cardiac failure at any time during the first study visit (Class III as per NYHA classification) or significant heart disease as judged by the physician

• Myocardial infarction during the last 6 months

• History of Mobitz Type II grade 2 AV block

• Past or current grade 3 AV block

• Confirmed history of sick sinus syndrome or sino-atrial heart block

• arrhythmia requiring current treatment with Class Ia drugs (disopyramide, procainamide, quinidine)

• hypertension uncontrolled with medication

5. History of malignancy of any organ system other than localized basal cell carcinoma of the skin.

6. Pregnant or nursing (lactating) women

7. Negative for varicella-zoster virus IgG antibodies at screening

8. History of previous fingolimod therapy

9. Presence of any clinically active infections

Investigational and reference therapy	Fingolimod

Efficacy assessments	EDSS, PASAT, SDMT, 9-hole peg test, timed 25-foot walk and relapse rate
Safety assessments	This study does not include any planned safety analysis
Other assessments	Not Applicable
Data analysis	Data analysis will be performed after all of the data is collected from the enrolled patients. All MS patients and control group will be accepted as the analysis sets. Cytokine and chemokine levels will be analyzed cumulatively at the end of the study. The results will be recorded to the blood sampling logs and laboratory logs cumulatively.
Key words	RRMS, Fingolimod, Cytokine, Chemokine

## 1 Introduction

### 1.1 Background

Multiple sclerosis (MS) is the leading cause of neurological disability in young adults and the most common demyelinating disorder of the central nervous system. It is widely regarded as a chronic autoimmune disorder encompassing both inflammatory (myelin destruction) and degenerative (axonal loss) features. Disease onset is thought to be mediated by T lymphocytes that recognize myelin antigens, cross the blood brain barrier and drive the immune response against oligodendrocytes and myelin sheaths. MS typically presents in relapsing forms, either with a relapsing-remitting (RRMS) or secondary progressive (SPMS) course. Patients suffer acute self-limiting attacks (relapses) of neurological dysfunction followed by complete or incomplete remission. Between relapses, patients are either neurologically and symptomatically stable (RRMS) or continue to deteriorate in function unrelated to relapses (SPMS). Currently available therapies for patients with RRMS (interferon  $\beta$  and glatiramer acetate) have partial efficacy (about 30-40% reduction in relapse rate and at best a modest effect on disability progression). These agents are biologic parenteral treatments requiring injections associated with side effects (injection site reactions, flu-like symptoms). Therefore, there is a strong medical need for a safe and effective oral treatment of MS.

Fingolimod is a novel, orally active, synthetic small molecule in clinical development for MS. Fingolimod is rapidly phosphorylated in vivo, and fingolimod-phosphate (fingolimod-P) acts as agonist of G protein-coupled receptors for sphingosine-1 phosphate (S1P). More particularly, fingolimod-P acts as 'super agonist' of the S1P1 receptor on thymocytes and lymphocytes, inducing internalization of that receptor. This renders these cells unresponsive to S1P1 signaling, thus depriving them of a signal necessary for egress from lymph nodes and secondary lymphoid tissues. The downstream result of this fingolimod induced interdiction of S1P1 signaling is a marked reduction in the number of both B and T lymphocytes in the intravascular compartment and a decrease in recirculation of these cells to extravascular compartments, including the CNS. In animal immunization models, fingolimod neither impaired T-cell activation, expansion, and memory, nor antibody production by B-cells. However, fingolimod will reduce the ability of an expanded number of activated effector lymphocytes to return to a site of inflammation or infection.

These effects on lymphocytes are believed to be linked to the efficacy of FTY720 in reducing inflammatory activity as seen in animal models of MS as well as in patients with relapsing MS. However, these effects may also lead to potential immunosuppression and an increased risk for infections. This risk may be further enhanced with the concomitant use of other immunosuppressants including corticosteroids.

Fingolimod has been shown to be highly active in a number of animal models for autoimmunity. In particular, fingolimod was highly effective both in a prophylactic and a therapeutic setting in several mouse and rat models of experimental autoimmune encephalomyelitis (EAE), an animal model of MS.

The clinical experience with fingolimod is already extensive. To date, over 12000 subjects (healthy volunteers, transplant patients and MS patients) have been exposed to single or multiple doses of fingolimod. Based on this experience, pharmacodynamic effects ascribed to

fingolimod are: 1) a rapid and persistent reduction of the peripheral lymphocyte count that is reversible after treatment discontinuation, 2) a predictable reduction in heart rate that is maximal upon treatment initiation and attenuates over time under continued treatment, 3) a mild- to moderate increase in airway resistance early after treatment initiation. The molecular basis of these effects is well understood and compatible with the known mode of action of fingolimod via engagement of S1P receptors.

An increased incidence of macular edema has been observed with fingolimod (in combination with cyclosporine A) in the renal transplantation studies. Regular ophthalmic monitoring in the ongoing clinical development program in MS patients has revealed cases of macular edema both prior to and after study drug initiation. The risk of macular edema in multiple sclerosis studies is currently under evaluation in the ongoing program, in which all patients are undergoing regular ophthalmology evaluations.

There is accumulating evidence that Th1 and Th17-type immunities play major roles in multiple sclerosis pathogenesis in the last decade. By contrast, Th2 and Treg cytokines appear to counterbalance the production of Th1 and Th17 cytokines and thus play an ameliorating role in the natural course of multiple sclerosis. Not surprisingly, many multiple sclerosis medications exert their beneficial effects through modulation of these cytokines. The effects of fingolimod on cytokine production are largely unknown.

## **1.2 Purpose**

The main purpose of this study is to measure the serum levels of major Th1, Th2, Th17 and Treg cytokines as well as cytokines and chemokines that are known to be upregulated during multiple sclerosis relapses. Measurements will be performed at 3 time points; i.e. before treatment, 12±1 weeks and 24±2 weeks after fingolimod treatment. By this way, we will be able to test whether fingolimod treatment shifts the cytokine balance from Th1/Th17 to Th2/Treg and reduces the levels of inflammation related cytokines and chemokines. The basal levels of the cytokines will be compared with the cytokine levels of healthy controls.

The second purpose of the study is to test the predictive value of cytokine/chemokine changes measured in the 3rd and 6th months on the EDSS, PASAT, SDMT, 9-hole peg test, timed 25-foot walk test and relapse rate observed after 6 months of treatment.

## **2 Study objectives**

### **2.1 Primary and key secondary objectives**

Primary objective of this study is:

-To evaluate the differences between serum cytokine and chemokine levels of healthy controls and multiple sclerosis patients

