### **2.2 Secondary objectives**

Secondary objective of this study is:

-To test the predictive value of cytokine/chemokine changes measured in the 3rd and 6th months on the PASAT, SDMT, 9-Hole peg test, timed 25-foot walk, EDSS and relapse rate observed after 6 months of treatment.

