### 3.2 Rationale of study design

This study design is not randomized or double blind, but it has no bias since the patients themselves will be their own controls if they fulfill the enrollment criteria.

This study was designed since there is accumulating evidence that Th1 and Th17-type immunities play major roles in multiple sclerosis pathogenesis in the last decade. By contrast, Th2 and Treg cytokines appear to counterbalance the production of Th1 and Th17 cytokines and thus play an ameliorating role in the natural course of multiple sclerosis. Not surprisingly, many multiple sclerosis medications exert their beneficial effects through modulation of these cytokines. The effects of fingolimod on cytokine production are largely unknown. So this study was designed to see to evaluate the effects of fingolimod on cytokine production.

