## **9.8 Sample size calculation**

Due to the lack of previous studies using all of the cytokines and chemokines and multitudinous analyses, it is difficult to estimate a precise sample size for our study. Despite this, our previous publications indicate that the basal IL-17 concentration is normally distributed with a mean of 32 pg/ml ( $\pm$ stdev of 15 pg/ml) in RRMS patients. If the true difference in the mean concentration of matched pairs is 7 pg/ml, we will need to study 50 pairs of subjects to be able to reject the null hypothesis with a power of 90%. The Type I error probability associated with this test of this null hypothesis is 0,05.

With assumption of drop out rate of 20% minimum 60 RRMS patients and 60 healthy control subjects should enroll to the study. Due to expected high rate of screen failure patients, we decided to screen 80 RRMS patients in order to reach 60 eligible RRMS subjects for the study.

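### Change on fingolimod is neither a primary nor a secondary objective, and the stated 90% power is for a paired test that the plan does not apply to its primary comparison

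*Protocol*

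**What the plan says.** **What the study is for.** The title is "Effects of Fingolimod (Gilenya®) on Cytokine and Chemokine Levels in Relapsing Remitting Multiple Sclerosis Patients". Protocol 1.2 says that with samples before treatment and at about 12 and 24 weeks "we will be able to test whether fingolimod treatment shifts the cytokine balance from Th1/Th17 to Th2/Treg". Protocol 3.2 adds that "this study was designed to see to evaluate the effects of fingolimod on cytokine production" and defends the non-randomised design on the ground that each patient serves as his or her own control.

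**What the objectives are.** The primary objective (synopsis, Protocol 2.1, SAP 3.1) is "To evaluate the differences between serum cytokine and chemokine levels of healthy controls and multiple sclerosis patients". It names no visit. The timing comes from Protocol 1.2: "The basal levels of the cytokines will be compared with the cytokine levels of healthy controls". The single secondary objective (Protocol 2.2, SAP 3.2) asks whether the month 3 and month 6 cytokine changes predict EDSS, PASAT, SDMT, 9-hole peg test, timed walk and relapse rate. It does not ask whether the levels change.

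**What is analysed.** SAP 6.5.1 and 6.5.2 list four contrasts for every marker: controls vs Visit 1, Visit 1 vs Visit 2, Visit 1 vs Visit 3, and controls vs Visit 3. None is ranked. Contrasts with controls use the Mann-Whitney or independent-samples t test; within-patient contrasts use the Wilcoxon or paired t test. Protocol 9.5 says that no special hypothesis is planned.

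**What the sample size rests on.** Protocol 9.8 and SAP 5.1 give basal IL-17 in RRMS patients a mean of 32 and an SD of 15 pg/ml, and continue: "If the true difference in the mean concentration of matched pairs is 7 pg/ml", 50 pairs of subjects give 90% power at a Type I error of 0.05. Allowing for 20% dropout, this becomes at least 60 patients and 60 controls.

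**The concern.** Two things do not line up.

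First, the question that justifies giving the drug and sampling at months 3 and 6 has no formal place among the stated objectives. If the control comparison is at baseline, as section 1.2 says, the study could meet its primary objective on Visit 1 samples alone and say nothing about fingolimod. A before/after finding would then come from one of several unranked contrasts.

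Second, the only power statement is for paired data, and the primary objective as the SAP analyses it is a comparison of independent groups. The eligibility criteria and the SAP describe no matching of patients to controls. A reader who takes the 90% as the power of the primary comparison would overestimate it.

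**Working it through.** **Inputs** (Protocol 9.8, SAP 5.1): difference 7 pg/ml, SD 15 pg/ml, alpha 0.05, power 90%, 50 pairs, 60 per group, 20% dropout (60 × 0.8 = 48). Sidedness is not stated; two-sided is assumed, because a one-sided test would need only 40 pairs and does not fit the stated 50.

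**1. Reproduce the plan's figure.** Paired formula: n = (SD_d × (1.960 + 1.282) / 7)², where SD_d is the SD of the within-pair difference. With SD_d = 15, n = 48.2, so 49 pairs, against 50 stated. By the noncentral t distribution with n − 1 degrees of freedom and noncentrality √n × 7/15, power is 89.9% at 50 pairs and 88.6% at 48. The figure reproduces as a paired test with SD_d = 15.

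**2. What SD_d = 15 requires.** The documents give 15 as the SD of the basal level, not of a difference. If both members of a pair have SD 15 and correlation ρ, then SD_d = 15 × √(2(1 − ρ)), which equals 15 only at ρ = 0.5. No correlation is stated, so a range is needed:

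| ρ (assumed) | SD_d | Pairs for 90% | Power at 48 pairs |
|---|---|---|---|
| 0 | 21.2 | 97 | 61% |
| 0.25 | 18.4 | 73 | 73% |
| 0.5 | 15.0 | 49 | 89% |
| 0.75 | 10.6 | 25 | 99% |

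(Pairs by the normal formula, power by the noncentral t.)

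**3. The primary contrast as the SAP tests it.** For two independent groups with SD 15 in each, n per group = 2 × (15 × 3.2415 / 7)² = 96.5, so 97 (98 by the t distribution). Power by the noncentral t with 2n − 2 degrees of freedom and noncentrality (7/15) × √(n/2):

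| Per group | Noncentrality | Power |
|---|---|---|
| 48 | 2.29 | 62% |
| 50 | 2.33 | 64% |
| 60 | 2.56 | 72% |

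Protocol 3.1 speaks of recruiting 80 patients, whereas 9.8 says that 80 are screened to reach 60. Even 80 patients against 60 controls would give 77%.

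**4. Purpose against objectives.**

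| Question | Where stated | Status |
|---|---|---|
| Patients vs controls, basal | Protocol 1.2, 2.1; SAP 3.1 | Primary |
| Do the changes predict clinical outcome? | Protocol 1.2, 2.2; SAP 3.2 | Secondary |
| Do levels change on fingolimod? | Title; Protocol 1.2, 3.2 | Neither; analysed in SAP 6.5 without rank |

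**The case against.** Several stronger readings are tempting, and the documents do not support them.

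- **That the 50 pairs are before/after pairs on fingolimod.** A reader might infer this, since it is the only contrast that is paired without matching. But the sample size sections mention neither fingolimod, nor visits, nor change from baseline. They speak of pairs of subjects and turn them into 60 patients and 60 controls, which fits patient-control pairs at least as well. Only the mismatch between a paired calculation and an unpaired test can be shown.
- **That no objective of any kind covers change on fingolimod.** The table of contents has a redacted entry directly after section 2.2, and its content is unknown. What can be verified is that the change is neither primary nor secondary.
- **That the primary objective excludes the drug, or concerns untreated patients.** The objective names no visit, the baseline timing comes from section 1.2, and the SAP also compares controls with Visit 3 patients on fingolimod. Patients may have had earlier MS drugs subject to washout, so the accurate term is before fingolimod.
- **That the before/after contrast has about 90% power.** That would treat 15 as the SD of differences, which the plan does not say.

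It is also fair to say that the before/after contrasts are not neglected: they are in the SAP with named paired tests, and the plan ranks none of its contrasts. With no hypothesis planned, the sponsor may regard the study as exploratory. That tempers the concern about rank. It does not make the stated 90% apply to the unpaired comparison, and it does not reconcile the purpose with the objectives.

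**Conclusion.** The concern holds in this form. The stated purpose and the stated primary and secondary objectives are misaligned: whether cytokine levels change on fingolimod is the declared reason for the study, yet it is neither a primary nor a secondary objective. The 90% power figure is arithmetically sound for 50 pairs if the SD of differences is 15, but it is not the power of the patient-control contrast as the SAP tests it. On the plan's own inputs that power is about 62% to 72% at 48 to 60 per group, a shortfall of 18 to 28 percentage points. Because the control comparison is at Visit 1 and controls are sampled once, later dropout matters little to it, so the upper end is the more likely value.

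The figures assume a two-sided test, an SD of 15 in both groups, normally distributed IL-17 and t tests. SAP 6.5.1 reports non-normal distributions and a Mann-Whitney test, so actual power could differ. Before/after power cannot be fixed without a within-patient correlation; it runs from 61% to 99% at 48 pairs over correlations from 0 to 0.75.

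**What to change.** 1. **Objectives (Protocol 2.1 and 2.2, SAP 3.1 and 3.2, synopsis).** Name the visit in the primary objective: Visit 1 patients vs controls. List change from Visit 1 to Visits 2 and 3 on fingolimod as an objective in its own right. Whether to make it primary, and with which marker and visit, is the sponsor's choice; the documents do not single out IL-17 at Visit 3. SAP 6.5 already speaks of distributions in the past tense, so if any marker data have been seen, the change should be dated and described accordingly.

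2. **Sample size (Protocol 9.8, SAP 5.1).** State which comparison the 50 pairs power and that 15 pg/ml is the SD of basal IL-17. Replace the 90% for the unpaired patient-control contrast with the power that it has (about 62% to 72% at 48 to 60 per group). For the before/after contrast, give power over a range of within-patient correlations (at 48 pairs: 61%, 73%, 89% and 99% for 0, 0.25, 0.5 and 0.75) instead of asserting that 15 is the SD of differences.

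The cost is an amendment of wording in both documents. No extra patients, visits or samples are needed. The drawback is a less favourable stated power for the control contrast.
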